5.1 Inclusion criteria

The Investigator will assess the eligibility of the patient and the study eye at the Screening visit and confirm eligibility at Baseline. Participants eligible for inclusion in this study must meet **all** of the following criteria:

1. Signed informed consent must be obtained prior to participation in the study.
2. Male or female patients ≥ 50 years of age at Screening.
3. Active CNV secondary to AMD that affects the central subfield, including retinal angiomatic proliferation (RAP) with a CNV component, confirmed by presence of active leakage from CNV seen by fluorescein angiography (FA) (or other imaging modalities) and sequelae of CNV, e.g. pigment epithelial detachment (PED), subretinal hemorrhage or subretinal pigment epithelium (sub-RPE) hemorrhage, blocked fluorescence, macular edema in the study eye at Screening.
4. Presence of intraretinal (IRF) and/or subretinal fluid (SRF) affecting the central subfield of the study eye as seen by SD-OCT in the study eye at Screening.
5. Best-corrected visual acuity (BCVA) score greater than or equal to 23 letters measured at 4-meters starting distance using Early Treatment Diabetic Retinopathy Study (EDTRS) visual acuity charts at both Screening and Baseline in the study eye.

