1.1. Changes from The Study Protocol

For SD-OCT parameters, in the study protocol, the Volume of Pigment-Epithelium Detachment (PEDs) defined as irregularly elevated lesions produced by the growth of the choroidal neovascular membrane and the accumulation of fluid or material in the sub-RPE space is planned to be evaluated as continuous variable (quantitative parameter). However, it was not possible to measure this volume according to the CRC evaluation. Consequently, the following qualitative parameters will be provided by CRC: the presence of PED will be summarized considering the possible values (i.e., 'No', 'Yes', 'UNG/P', 'UNG/Q') and in case of PED presence, a description of the type of PED will be provided considering the predominant feature as fibrovascular only, predominantly fibrovascular, purely serous, predominantly serous, drusenoid PED, UNG/P, UNG/Q.

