For what concern the LOCF approach reported in the study protocol, this approach will be maintained for the predictors to be included in the analysis of the primary endpoint since the focus is on the first visits (from baseline to Week 16) and all enrolled patients should perform these visits independently of treatment regimen that will be followed by each patient. For the secondary endpoints, LOCF approach will not be applied because after Week 16 each patient will have different scheduled of visits based on treatment regimen. The LOCF approach can be considered only until Week 16 but (1) for OCTA the number of missing data will lead to most data imputed than the one observed, (2) for SD-OCT the approach is applied in the analysis of primary endpoint, (3) for BCVA the LOCF approach will be provided until Week 16, (4) for HAD and EQ-5D-5L questionnaires the LOCF approach will not be applied since only two assessments of these questionnaires are planned in the study.

As performed for interim analysis, all analysis will be conducted on Safety population since during the interim analysis, in which all enrolled patients were considered (see section 6.6 for further details), the FAS and Safety populations include the same set of patients since per definitions of the study protocol, the FAS considered all enrolled patients who completed the baseline visit and all of them are treated and consequently all of them belong to Safety population.

The evaluation of prevalence of anxiety and depression will be performed only based on HAD questionnaire and not based in terms of treatment that patients could have received for anxiety/depression.

The following additional analysis will be included:

- SD-OCT parameters at baseline and type of predominant lesion will be also analyzed according to BCVA groups and CST groups based on changes at Week 12 in patients who performed Week 16 and were still on treatment at this timepoint.
- A graphical representation of BCVA ETDRS score and CST by means of spaghetti plot will be provided.
- Analyses on CST and BCVA will be also performed on patients with BCVA ETDRS score lower than 69 letters at baseline.

| | |
|--|----------------------------------|
| | Statistical Analysis Plan |
| | Sponsor: Novartis |
| | Protocol: CRTH258AIT04 |

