6.3. Efficacy Evaluation

6.3.1. Primary efficacy analysis

Definition of primary endpoint

The primary aim of the study is to assess which early anatomical parameters measured by multimodal imaging at each visit from Baseline to Week 16, predict in brolucizumab-treated participants with wAMD the q12w fluid-free response at Week 48.

The primary estimand of the study is to identify the q12w fluid-free predictive factors.

Patient will be classified as follows for the outcome of interest:

- **q12w fluid-free:** patients completing the treatment and the study maintaining a stable q12w regimen assigned at Week 16 up to Week 48 and without the presence of IRF and SRF at Week 48 according to SD-OCT grading.
- **not q12w fluid-free:**
 - patient who completes the treatment and the study with the presence of IRF or the presence of SRF at Week 48 according to SD-OCT grading;
 - patient who followed the q8w regimen of treatment at any time during the study (considering also who started with q12w regimen but then due to disease activity shifted to q8w regimen);
 - patient who discontinued treatment at any time after baseline since also the discontinuation from the treatment can be considered as intercurrent event and according to data handling rules should be considered as 'failure'.
 - patient who dropped out at any time after baseline since the discontinuation from the study is considered as intercurrent event and according to data handling rules should be considered as 'failure'.

The following qualitative and quantitative anatomical parameters measured by FA, ICGA, CFP and SD-OCT will be considered as potential predictive factors in the statistical model and, when measured at more than one timepoint, categories variables based on their changes between baseline and Week 16 will be created as described below:

| | |
|--|---|
| | Statistical Analysis Plan |
| | Sponsor: Novartis Protocol: CRTH258AIT04 |

| Variable | Timing of data collection | Source | Categories used in the model | Reference value for the model |
|----------------------------------|---|--|--|-------------------------------|
| Type of predominant CNV lesion | Screening | CRC grading based on SD-OCT, FA, ICGA and CFP at Screening | Type I, Type II, Type III, PCV, UNG/P or UNG/Q. Of note, Type I and PCV will be considered as unique category while UNG/P and UNG/Q will be considered as missing data. | Type I + PCV |

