| subRPE fluid | Baseline, Week 4, Week 8, Week 12 and Week 16 | SD-OCT grading | Stable absent (i.e., all measurement 'No'), Stable present (i.e., all measurement 'Yes'), Improved (i.e., last measurement collected as 'No' and baseline 'Yes'), Worsened (i.e., last measurement collected 'Yes' and baseline 'No'). | Stable absent |
| SHRM | Baseline, Week 4, Week 8, Week 12 and Week 16 | SD-OCT grading | Stable absent (i.e., all measurement 'No'), Stable present (i.e., all measurement 'Yes'), Improved (i.e., last measurement collected as 'No' and baseline 'Yes'), Worsened (i.e., last measurement collected 'Yes' and baseline 'No'). | Stable absent |
| ORT | Baseline, Week 4, Week 8, Week 12 and Week 16 | SD-OCT grading | Stable absent (i.e., all measurement 'No'), Stable present (i.e., all measurement 'Yes'), Improved (i.e., last measurement collected as 'No' and baseline 'Yes'), Worsened (i.e., last measurement collected 'Yes' and baseline 'No'). | Stable absent |
| ELM integrity loss in center 1mm | Baseline, Week 4, Week 8, | SD-OCT grading | Stable absent (i.e., all measurement 'No'), Stable present (i.e., all measurement | Stable absent |

| | |
|--|----------------------------------|
| | Statistical Analysis Plan |
| | Sponsor: Novartis |
| | Protocol: CRTH258AIT04 |

| | | | | |
|-------------|---|----------------|--|---------------------------|
| | Week 12 and Week 16 | | 'Yes'), Improved (i.e., last measurement collected as 'No' and baseline 'Yes'), Worsened (i.e., last measurement collected 'Yes' and baseline 'No'). | |
| Type of PED | Baseline, Week 4, Week 8, Week 12 and Week 16 | SD-OCT grading | Stable Fibrovascular only (i.e. all measurement 'Fibrovascular only'), Stable not only fibrovascular (i.e. all measurement 'Predominantly fibrovascular' or 'Predominantly serous' or 'Drusenoid PED'), 'From Fibrovascular only to not only fibrovascular' (i.e., last measurement collected 'Predominantly fibrovascular' or 'Predominantly serous' or 'Drusenoid PED' and baseline 'Fibrovascular only'),), 'From not only fibrovascular to Fibrovascular only' (i.e., last measurement collected 'Fibrovascular only' and baseline 'Predominantly fibrovascular' or 'Predominantly serous' or 'Drusenoid PED'). | Stable Fibrovascular only |
| CST (μm) | Baseline, Week 4, Week 8, Week 12 and Week 16 | SD-OCT grading | Percentage changes in CST vs baseline at the last measurement collected. | NA |

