NA=Not Applicable; CNV=Choroidal Neovascularization; UNG/P=Ungradable due to pathology; UNG/Q=Ungradable due to quality SHRM=Subretinal hyper reflective materia; ORT=Outer retinal tubulation; ELM=External Limiting Membrane; CST=Center Subfield Thickness; PED=Pigment Epithelial Detachment.

Of note, for each variable 'Missing' values can be present in case that images are collected but not graded by Central Reading Center (CRC) since they are collected by means of a not certificated instrument.

| | |
|--|----------------------------------|
| | Statistical Analysis Plan |
| | Sponsor: Novartis |
| | Protocol: CRTH258AIT04 |

Analysis methodology

Firstly, the proportion of patients with and without q12w fluid-free will be provided and then a descriptive summary table by q12w fluid-free and not q12w fluid-free will be provided for each variables described in table above.

A logistic models will be performed for each one of the variables listed above considering as outcome the patients' classification in q12w fluid-free and not q12w fluid-free.

Multivariable logistic model will be performed considering as outcome the patients' classification in q12w fluid-free and not q12w fluid-free and as covariates all the variables with $p<0.10$ in the previous analysis. Results of logistic models will be presented in terms of beta coefficient and standard error, Odds Ratio and relative 95% Confidence interval and p-value.

All these analyses will be performed on Safety population.

Data handling rules

In case of patients who dropped out at any time after baseline, the primary outcome cannot be evaluated since the patient status related to treatment regimen and presence of IRF o SRF at Week 48 are not observed. The dropped-out patients constitute intercurrent event and they will be considered a not q12w fluid-free at Week 48. Similarly, in case of patients who discontinued the treatment at any time after baseline, the primary outcome cannot be totally evaluated since the patient treatment regimen at q12w cannot be observed until Week 48. The patients who discontinued treatment constitute intercurrent event and they will be considered a not q12w fluid-free at Week 48.

Sensitivity of primary analysis

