- In the study protocol, the Volume of Pigment-Epithelium Detachment (PEDs) defined as irregularly elevated lesions produced by the growth of the choroidal neovascular membrane and the accumulation of fluid or material in the sub-RPE space. On SD-OCT, PEDs appear as broad elevations of the RPE

| | |
|--|----------------------------------|
| | Statistical Analysis Plan |
| | Sponsor: Novartis |
| | Protocol: CRTH258AIT04 |

band relative to Bruch's membrane. The volume of PEDs is considered as a quantitative parameter evaluated by SD-OCT. However, it was not possible to measure this volume according to the CRC evaluation. Consequently, the following qualitative parameters will be provided: the presence of PED will be summarized considering the possible values (i.e., 'No', 'Yes', 'UNG/P', 'UNG/Q') and in case of PED presence, a description of the type of PED will be provided considering the predominant feature as fibrovascular only, predominantly fibrovascular, purely serous, predominantly serous, drusenoid PED, UNG/P, UNG/Q.

In addition, the following quantitative parameter will be measured:

- Central Retinal Thickness (CRT) measurement, as main quantitative morphological parameter of wAMD. The CRT evaluated in this study represents the average retinal thickness of the circular area within 1 mm diameter around the foveal center and it will be called as Center Subfield Thickness (CST) also known as foveal thickness and it will be measured in μm .

Analysis methodology

Firstly, a description for the SD-OCT images' quality will be provided at each visit reporting the proportion of images with quality concerns present and a description of the issue detected that could be one or more of the following:

- HIGH SPEED NOT HIGH RESOLUTION
- VOLUME SCAN ABSENT
- VOLUME SCAN INCOMPLETE
- RASTER/LINE SCAN ABSENT
- RASTER/LINE SCAN INCOMPLETE
- OFF-FOVEA
- MOTION ARTIFACT
- SCAN CLIPPING
- DEGRADED IMAGE
- POOR CONTRAST
- OTHER/ADDITIONAL DETAILS

Similarly, the proportion of images with quality concerns that prevent any grading is provided together with the issue(s) detected (one or more than one among the list previously described).

All qualitative and quantitative parameters described above will be described overall at each visit in terms of absolute and relative frequencies or as continuous variable, respectively.

| | |
|--|----------------------------------|
| | Statistical Analysis Plan |
| | Sponsor: Novartis |
| | Protocol: CRTH258AIT04 |

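### Read literally, the predictor table in SAP 6.3.1 leaves some validly graded eyes without a level in five of the seven candidate predictors of the primary models

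*SAP*

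**What the plan says.** SAP 6.3.1 lists seven candidate predictors of the q12w fluid-free outcome: predominant CNV lesion type, sub-RPE fluid, SHRM, ORT, ELM integrity loss, type of PED and CST. All but CNV type are read at Baseline and Weeks 4, 8, 12 and 16. The text above the table says that repeatedly measured variables are categorised by their change from baseline to Week 16.

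For the four yes/no variables the table gives "Stable absent (i.e., all measurement 'No'), Stable present (i.e., all measurement 'Yes'), Improved (i.e., last measurement collected as 'No' and baseline 'Yes", and Worsened for a last reading of Yes after a baseline No.

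For type of PED there are two stable groups and two transitions between them. The first group is fibrovascular only. The second is "Stable not only fibrovascular (i.e. all measurement 'Predominantly fibrovascular' or 'Predominantly serous' or 'Drusenoid PED". The reading centre's own list of types is longer: "fibrovascular only, predominantly fibrovascular, purely serous, predominantly serous, drusenoid PED, UNG/P, UNG/Q" (SAP 1.1). Absence of PED is also a possible grade: "the presence of PED will be summarized considering the possible values (i.e., 'No', 'Yes', 'UNG/P', 'UNG/Q" (SAP 6.3.2.2).

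Each predictor enters its own logistic model. Those with p<0.10 go into the multivariable model.

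**The concern.** A categorical predictor needs a level for every eye that has valid grades. Here *stable* requires all readings to agree, and the two change levels require the last reading to differ from baseline. Eyes that change and come back fall between the two. The PED row also omits two states that the reading centre records. PED is not required for entry: Protocol 5.1, criterion 3, names it only as an example among "sequelae of CNV, e.g. pigment epithelial detachment (PED), subretinal hemorrhage or subretinal pigment epithelium (sub-RPE) hemorrhage, blocked fluorescence, macular edema".

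An eye without a level either drops out of that predictor's model, and of any multivariable model that keeps the predictor, or is placed by a programming choice that nobody has written down. The SAP states the exclusion of patients with a missing covariate only for the weighted sensitivity analysis. For the primary models it follows from how logistic regression is ordinarily fitted.

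The loss need not be neutral. Take sub-RPE fluid present at baseline, absent through Week 12 and present again at Week 16. Protocol 6.7.2 lists this fluid among the parameters for judging disease activity at Week 16. Activity can lead to a q8w regimen, and any q8w period makes the patient not q12w fluid-free. So an unplaced pattern may be related to outcome; the documents do not show that it is.

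**Working it through.** **Inputs.** Level definitions and the five visits: SAP 6.3.1 table. PED grades: SAP 1.1 and 6.3.2.2. Enrolled patients: 122 (SAP 1.1). The plan gives no figure for how many eyes its levels cover, so there is none to reproduce. Its precision figures do reproduce, (2 × 1.96 / 0.12)² × 0.56 × 0.44 = 262.9, rounded up to 263, and 2 × 1.96 × √(0.25/122) = 17.74%, but they do not bear on this point.

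**1. Yes/no predictors.** With k graded visits there are 2^k sequences. Two are constant, 2^(k−2) are Improved and 2^(k−2) are Worsened. The number without a level is 2^k − 2 − 2 × 2^(k−2) = 2^(k−1) − 2.

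| Graded visits | Sequences | Without a level |
|---|---|---|
| 5 | 32 | 16 − 2 = 14 |
| 4 | 16 | 8 − 2 = 6 |
| 3 | 8 | 4 − 2 = 2 |
| 2 | 4 | 2 − 2 = 0 |

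All 14 end where they began. Fluctuation alone is not the problem: of the 22 five-visit sequences with two or more changes, 8 end in a different state and are classified; the other 14 are not.

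**2. Type of PED.** There are six gradable states, absent plus five types, so 6 × 6 = 36 baseline/last pairs.

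- If absent counts as a measurement, only pairs within the four named types can have a level: 4 × 4 = 16. The other 20 cannot: 11 involve absent PED (6 + 6 − 1) and 9 more involve purely serous (5 + 5 − 1).
- SAP 1.1 and 6.3.2.2 describe type only when PED is present. If type is therefore collected only then, the 8 pairs with a named type at one end and absent PED at the other can have a level. That leaves 20 − 8 = 12: 1 absent/absent (taken as no PED throughout), 2 absent/purely serous and 9 other purely serous pairs.
- Of the 16 pairs within the named types, the 10 in the same group (1 + 9) have a level only if every visit in between stays in that group. With just the two groups, 14 of 32 five-visit sequences have none, as in step 1.

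**3. Do other rules place these eyes?**

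- LOCF, of which SAP 1.1 says "this approach will be maintained for the predictors to be included in the analysis of the primary endpoint", repeats a grade already present. With baseline observed and four follow-ups each Yes, No or missing there are 2 × 3⁴ = 162 patterns, and LOCF changes whether an eye has a level in 0 of them.
- The note under the table, "for each variable 'Missing' values can be present in case that images are collected but not graded by Central Reading Center (CRC", is about ungraded images.
- The rule that "UNG/P and UNG/Q will be considered as missing data" stands in the CNV row and is about ungradable images.

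None of these covers an eye with valid grades.

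**4. Illustration only.** The share of affected eyes is not in the documents. If 5%, 10%, 20% or 30% of eyes were unplaced on a predictor (assumed) and dropped, its model would keep 122 × (1 − share) = about 116, 110, 98 or 85. A model holding all five predictors would keep the same numbers if the same eyes were affected each time, and 122 × (1 − share)⁵ = about 94, 72, 40 or 20 if the gaps were independent.

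**The case against.** The sentence above the table speaks of change between baseline and Week 16. On that basis *stable* could mean no net change, and the gap for the yes/no variables would be a slip that one line cures. That may well be the intent, but the definitions say that all measurements must agree, and a programmer following them would leave these eyes out. The reading also does nothing for purely serous PED or for eyes that never had PED.

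One could say that absent PED is simply not applicable to a variable about type. No rule says so, and these eyes would then leave the PED model without a stated N.

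Some reporting already exists: descriptive tables by outcome (6.3.1), percentages that count the missing category (4.1) and shift tables for the four yes/no variables (6.3.2.2). This stands in part. But eyes coded as missing for want of a level would be mixed with ungradable ones, and the N of the multivariable model is not required.

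Finally, the interim analysis covered all 122 patients up to the last patient's Week 16 (SAP 6.6), and the SAP's document history shows that 6.3.1 was later changed to change-based predictors. The levels may have been fitted to the observed grades, and some unlisted cells may be empty. The SAP does not say, so this cannot be confirmed or ruled out.

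**Conclusion.** The table is wrong as written for five of seven predictors; CNV type and CST are not affected. The gap is 14 of 32 five-visit sequences for each yes/no predictor. For PED it is 20 or 12 of 36 baseline/last pairs, according to how absence is read, plus the same change-and-return gap. The yes/no count rests on taking the words about all measurements literally. The omission of purely serous PED and of eyes without PED throughout does not depend on that.

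A reader might infer that 14/32 = 44% of eyes are lost, or that more than half of PED data are unusable. The documents do not support this: the counts treat possible patterns as equally likely, and no patient frequencies are given. Nor do they show that the primary result is biased. What is established is that the stated rule, applied as it stands, removes validly graded eyes from the primary models and from the p<0.10 screen, in a trial that enrolled 122 of a planned 263. Each eye lost is 1/122 = 0.8% of the sample. Classification of the outcome itself is unaffected. This should be corrected, since the remedy is cheap and the actual counts can be read from existing grades.

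**What to change.** In the SAP 6.3.1 table:

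1. **Yes/no predictors.** Define the four classes from baseline and last gradable value only: No/No, Yes/Yes, Yes/No, No/Yes. Each takes 8 of the 32 five-visit sequences, so all are covered with no added parameters. This matches the stated aim of capturing change to Week 16, the CST row of the same table and the planned shift tables.
2. **Type of PED.** Also use baseline and last gradable visit. Add purely serous to the not-only-fibrovascular group and add a no-PED level. That covers 5 × 5 + 1 = 26 of 36 pairs. The other 10 are PED that resolves (5) and PED that is new (5); state in advance, without reference to outcome, how each is classified.
3. **Reporting.** Give the N used in every single-variable and multivariable model, with unclassified eyes shown separately from missing or ungradable ones.

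The cost is SAP wording and a re-derivation from grades already held; no new data are needed. Change-and-return eyes are pooled with stable ones, so describe them separately by outcome. A separate level for them would also be exhaustive, at the price of one more parameter per predictor. The no-PED level adds one parameter. Eyes with an ungradable baseline remain missing, because SAP 6.3.2.2 says that screening SD-OCT images are stored but not graded.

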12.4.5 Sensitivity analyses for primary endpoint/estimand

A sensitivity analysis on the primary model will be performed using the LOCF approach in case of missing SD-OCT or OCTA evaluations between Week 4 and Week 16.

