3.5. Sample Size and Power Estimation

The sample size calculation is based on the assumption of an expected percentage of participants who have maintained the q12w regimen up to Week 48 equal to 56%, as derived from the HAWK study, and the hypothesis of a maximum percentage of not-fluid free participants out of these q12w-regimen participants at Week 48 equal to 18%. Therefore, the percentage of responders, defined as fluid-free participants who have maintained a q12w stable regimen up to Week 48, could range between 56% to 46%.

[figure not shown]
Considering a percentage of responders of 56% and a maximum width of the 95% confidence interval of 12%, 263 patients should be enrolled. Applying the rules of thumb, with 263 patients and a percentage of responders of 56%, a maximum number of 12 covariates can be included in the multivariate regression model (Harrell, 2015). As shown in Figure 2.5-1, the precision of the estimate remains stable around 12%, considering a percentage of responders ranging between 56% to 46%. Similar considerations can be made with a number of covariates that remains equal to 12.

Finally, to account for a screening failure rate of 12%, a total of approximately 300 participants should be screened in order to enroll 263 evaluable participants.

The sample size calculations were performed with nQuery 7.0.

| | |
|--|----------------------------------|
| | Statistical Analysis Plan |
| | Sponsor: Novartis |
| | Protocol: CRTH258AIT04 |

[figure not shown]
Figure 2.5-1: Precision of the estimate scenario

Since the enrolment was closed with less than 263 enrolled patients, the precision of the 95% CI will be re-computed based on the effective number of patients evaluable for the primary endpoint of the study.

Based on interim analysis, 122 enrolled patients will be available and consequently, the Figure above is recomputed according to the effective number of enrolled patients and provided below in Figure 2.5-2:

Figure 2.5-2: Precision of the estimate scenario re-computed

Based on different scenario of expected proportion between 46% to 56% and the effective number of 122 enrolled patients, the maximum width that can be observed will be of 17.74%.

| | |
|--|---|
| | Statistical Analysis Plan |
| | Sponsor: Novartis Protocol: CRTH258AIT04 |

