4. DEFINITIONS AND GENERAL METHODOLOGY

4.1. General Methodology

Statistical tables, listings and analyses will be produced using SAS® release 9.4 (64 bit) or later (SAS Institute, Inc., Cary, NC, USA).

The data from all sites will be pooled and summarized.

Continuous data will be summarized with mean, standard deviation (SD), median, Q1, Q3, minimum and maximum. Categorical data will be presented by absolute and relative frequencies (n and %) or contingency tables. The percentage calculation will be based on total values (i.e., count will be shown also in the missing category, unless otherwise specified).

Unless stated otherwise, a two-sided alpha level 0.05 will be considered. No alpha level adjustment will be carried out for primary and secondary outcome variables, unless otherwise specified.

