The cumulative incidence rate of patients with sustained dryness from Week 8 up to Week 48 will be summarized together with 95% confidence interval (CI) using the Clopper-Pearson method. A graphical representation (bar graph) will be also provided.

The median time to achieve sustained dryness and its corresponding two-sided 95% confidence interval (CI) will be estimated using the Kaplan-Meier product-limit method. Reverse Kaplan-Meier plot will be also presented.

Data handling rules

An observed approach will be considered.

Sensitivity of secondary analysis

Not applicable.

| | |
|--|----------------------------------|
| | Statistical Analysis Plan |
| | Sponsor: Novartis |
| | Protocol: CRTH258AIT04 |

6.3.2.5. Reason underlying the Investigators' choice of brolucizumab treatment regimen at Week 16

Definition

As previously investigated during the interim analysis, the reasons underlying the Investigators' choice of brolucizumab treatment regimen at Week 16 will be analyzed.

According to SmPC of brolucizumab, after the loading phase of treatment (i.e., first 3 injection every month) at Week 16 the investigator should choice the treatment regimen for each patient between the q12w or the q8w regimen. This choice should be based on the presence/absence of disease activity evaluated according to different parameters.

Analysis methodology

Considering the safety set and the number of patients who performed Week 16 and were still on treatment, a description of the total number of parameters considered to assess the presence or absence of disease activity at Week 16 will be provided in terms of continuous variable and frequencies of each combination of parameters considered to assess disease activity will be also provided (e.g., BCVA+CSR, CST+IRF and so on). Considering the total number of patients who performed Week 16 and were still on treatment, the proportion of patients for whom their disease activity is evaluated by means of each one of the following parameters is summarized:

- BCVA
- Leakage at FA/ICGA
- Central Subfield Thickness (CST) at SD-OCT
- Intraretinal fluid (IRF) at SD-OCT
- Subretinal fluid (SRF) at SD-OCT
- Subretinal pigment epithelium (sub-RPE) fluid at SD-OCT
- Retina Pigment Epithelial Detachment volume at SD-OCT
- Central Retinal Thickness (CRT)
- Subretinal hyperreflective material (SHRM) at SDOCT
- CNV size at OCTA
- Vessel density at OCTA
- Vessel morphology at OCTA
- Hemorrhage at CFP
- Other

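### Patients who leave the study before Week 16 are failures by rule and have their SD-OCT predictors read early, so the primary models can show an association created by early exit alone

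*SAP*

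**What the plan says.** **Outcome.** Under SAP 6.3.1 a responder must complete treatment and study on a q12w regimen assigned at Week 16, without IRF or SRF at Week 48. Failures include a "patient who dropped out at any time after baseline since the discontinuation from the study is considered as intercurrent event". Stopping treatment at any time after baseline is also a failure. All the models use the Safety population, and SAP 4.4.3 keeps drop-outs in on whatever assessments they have.

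**Predictors.** The table in SAP 6.3.1 takes CST as "Percentage changes in CST vs baseline at the last measurement collected". The yes/no findings (sub-RPE fluid, SHRM, ORT, ELM loss) are classed by comparing baseline with the last scan, or by whether all scans agree. PED type is handled in the same way. No minimum visit is set.

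**LOCF.** SAP 1.1 says that "this approach will be maintained for the predictors to be included in the analysis of the primary endpoint". In Protocol 12.4.5 it had a smaller role: "A sensitivity analysis on the primary model will be performed using the LOCF approach", for scans missing between Week 4 and Week 16. The SAP plans no primary model without it.

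**Selection.** The multivariable model takes "as covariates all the variables with $p<0.10$ in the previous analysis".

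**A Week 16 set used elsewhere.** The regimen-choice analysis in SAP 6.3.2.5 is restricted: "Considering the safety set and the number of patients who performed Week 16 and were still on treatment".

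**The concern.** For a patient who leaves the study before Week 16, the time of exit acts on both sides of the regression. It fixes the outcome as failure, because no regimen was ever assigned at Week 16. It also fixes how early the predictor is read. Someone whose last scan is at Week 4 is read after one injection, whereas someone who stays is read at Week 16, after three. If CST is still falling over those weeks, leavers contribute small falls paired with certain failure, and a small fall then looks like a predictor of failure with no biological relation behind it.

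The study is meant to find early imaging signs that could support the q12w or q8w choice, which is first made at Week 16. Patients already gone face no such choice, yet they can help to decide which variables pass the screen and are reported.

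Patients who only stop treatment raise a different problem. They should still be scanned up to Week 16, so they contribute off-treatment anatomy paired with a rule-assigned failure.

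**Working it through.** **1. The plan's own figures.** From SAP 3.5, n = 4 × 1.96² × 0.56 × 0.44 / 0.12² = 262.9, so 263. The maximum width with 122 patients is 2 × 1.96 × √(0.25/122) = 17.74%. Both reproduce. They describe the precision of the response proportion and say nothing about the predictor models.

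**2. Inputs.** From the documents: N = 122, responders 46% to 56%, screen at p<0.10, two-sided alpha 0.05. Assumed, because the documents do not give them: the number of exits before Week 16, the time of their last scan, and the course and spread of CST.

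**3. Simulation A: fixed numbers of leavers.** The model is logit P(response) = β0 + β1 × (% CST change). Response is unrelated to CST among those who stay (about 51% respond; CST change mean -30%, SD 20%). Leavers are set to failure. The chance that CST passes p<0.10 should be 10%.

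| Leavers' CST change | Gap in mean from stayers | 6 leavers (4.9%) | 9 (7.4%) | 12 (9.8%) |
|---|---|---|---|---|
| 80% of full | 6 points | about 9.5% | about 10% | about 11% |
| Half | 15 points | about 12% | about 14% | about 18% |
| None (baseline scan only, coded 0%) | 30 points | about 20% | about 29% | about 43% |

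Repeat runs put the first row at 9-11% and the second at 10-21%. Three baseline-only leavers give about 11.5%.

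**4. Simulation B: shape of the CST course.** N = 122, 50% responders overall, SD 15 points. Of the leavers, 20% have only a baseline scan; the rest have a last scan at Week 4, 8 or 12 with equal chance.

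| Mean CST change at Baseline, W4, W8, W12, W16 (%) | Leavers' mean | p<0.10 at 2%, 5%, 10%, 15% exits | Median OR per 10 points |
|---|---|---|---|
| Gradual: 0, -12, -20, -25, -28 | 0.8 × (-19.0) = -15.2 | 10%, 13%, 22%, 36% | 0.98 to 0.86 |
| Fast then flat: 0, -25, -28, -28, -28 | 0.8 × (-27.0) = -21.6 | 10%, 12%, 14%, 17% | 0.99 to 0.92 |
| Rebound: 0, -22, -28, -30, -24 | 0.8 × (-26.7) = -21.3 | 10-11% throughout | 1.00 to 0.97 |

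In the gradual case at 10% exits, moving the baseline-only share from 0 to 40% moves the pass rate from 16% to 31%. In the rebound case with no baseline-only leavers, the leavers' mean would be -26.7%, a deeper fall than the -24% at Week 16. The bias would then run the other way.

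**5. A yes/no finding.** Assume 10% exits timed as in step 4, and a finding present at baseline that clears in 30%, 45%, 50% and 50% by Weeks 4, 8, 12 and 16, unrelated to response. Stayers respond with probability 0.5/0.9 = 0.556.

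- Leavers coded *Improved*: 0.0267 × (0.30 + 0.45 + 0.50) = 0.033. Leavers coded *Stable present*: 0.100 - 0.033 = 0.067.
- P(response | *Improved*) = 0.45 × 0.556 / (0.45 + 0.033) = 0.517.
- P(response | *Stable present*) = 0.45 × 0.556 / (0.45 + 0.067) = 0.484.
- The odds ratio between them is 1.14. It is 1.03, 1.07 and 1.22 at 2%, 5% and 15% exits.

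The SAP's reference is *Stable absent*. If absent findings stay absent, response there is 0.50, and the SAP's contrasts are 0.517/0.483 = 1.07 and 0.484/0.516 = 0.94.

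**6. Restricting to Week 16.** With the simulation B model fitted only in patients still present and on treatment at Week 16, the pass rate is 9-12% at p<0.10 and 4-7% at p<0.05, and the median OR is about 1.00, in every scenario.

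**The case against.** A reader might infer that everyone who stops treatment early has a shortened predictor. The documents do not support that. Protocol 9.1.1 asks patients who stop before Week 16 to keep monthly visits up to Week 16, and Table 8-1 schedules SD-OCT at each. Attendance is discretionary, but no rule cuts their series short.

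A reader might also take 43% as the likely error rate. That needs 12 leavers, all with only a baseline scan coded as 0%. Protocol section 8 asks study leavers to return for the final-visit assessments, which should make baseline-only series uncommon. The SAP never says that such a patient counts as 0% or *Stable*. If they count as missing, they drop out of the model.

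The weighted model in SAP 6.3.1 is fitted in complete participants, so study leavers are out of it. That is a real partial check. However, it keeps the covariates already chosen by the p<0.10 screen, and patients who stopped treatment but completed the study remain in it as failures. It cannot undo a selection driven by early exit.

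Finally, counting drop-outs as failures was prespecified (Protocol 12.4.1 to 12.4.3), and the SAP discloses its extension to treatment stops. Restricting to Week 16 conditions on a post-baseline event and narrows the population. This objection stands, and it is the reason to show both fits.

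**Conclusion.** The concern holds in a limited form. The mechanism follows from the text for patients who leave the study before Week 16: failure is certain and the predictor may be read early. The primary models can therefore contain an association made by early exit. The documents do not show that they do.

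The effect is negligible at about 2% exits, or when leavers already show most of the CST change. It is material at about 10% exits or more with a gradual CST fall, or when several leavers have only a baseline scan coded as no change. All of these sizes rest on assumed exit numbers, scan timing and CST courses. The direction is not fixed either: it would be wrong to conclude that the bias always favours improvement, since a rebound by Week 16 can cancel or reverse it.

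The remedy is cheap and restores roughly nominal error in simulation, so the change is worth making although the size is uncertain.

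**What to change.** In SAP 6.3.1:

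- Repeat the whole procedure, both the univariable screen at p<0.10 and the multivariable model, in Safety Set patients who attended Week 16 and were still on treatment (the set in SAP 6.3.2.5). Make this the predictor analysis, or at minimum a key sensitivity analysis beside the all-patient model.
- Within that set, use LOCF only for isolated missing or ungradable scans.
- State that patients with only a baseline scan are not coded as 0% change or *Stable*.
- Report the number of exits before Week 16 by last scan available. The interim cut-off was set at the last enrolled patient's Week 16 visit (SAP 6.6), so this can be counted.
- Keep early leavers as failures in the overall response proportion.

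The cost is SAP wording and one further model run on a set already described. A few patients leave the predictor models, and the results then apply to patients still on treatment at Week 16.
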